6.4.2. Additional considerations**6.4.2.1. Combined Solicited and Unsolicited Adverse Events**

For clintrials.gov and EudraCT posting purposes, a summary of combined solicited and unsolicited non-serious adverse events will be produced by System Organ Class and preferred terms and according to occurrence of each event.

A summary of subjects with all combined solicited (regardless of their duration) and unsolicited adverse events will be provided. Solicited adverse events will be coded by MedDRA as per the following codes.

Solicited symptom	Lower level term code	Corresponding Lower level term decode
PA	10022086	Injection site pain
RE	10022098	Redness at injection site
SW	10053425	Swelling at injection site
TE	10016558	Temperature/Fever
FU	10022998	Irritability/Fussiness
DR	10013649	Drowsiness
LO	10003028	Loss of appetite

7. ANALYSIS INTERPRETATION

All analyses will be conducted in a descriptive manner.

8. CONDUCT OF ANALYSES

Any deviation(s) or change(s) from the original statistical plan outlined in this protocol will be described and justified in the final study report.

8.1. Sequence of analyses

The final analyses of all data will be conducted when all data are available. This analysis will include the final analysis of immunogenicity and the final analysis of solicited and unsolicited symptoms and SAEs. A clinical study report containing all data will be written and made available to the investigators.

Description	Analysis ID	Disclosure Purpose (CTRS=public posting, SR=study report, internal, public posting)	Dry run review needed (Y/N)	Study Headline Summary (SHS)requiring expedited communication to upper management (Yes/No)	Reference for TFL
Final	E1_01	SR	Yes	Yes	TFL TOC

8.2. Statistical considerations for interim analyses

NA

9. CHANGES FROM PLANNED ANALYSES

- During the course of the study, the assays used to measure the anti-D, anti-T, anti-PT, anti-FHA and anti-PRN IgG concentrations were re-developed and re-validated and both assay units and assay cut-offs were adapted. The new ELISA's for PT, FHA and PRN were calibrated against the WHO International Standard (NIBSC 06/140). This allowed the expression of concentrations measured with the new ELISA's in international units per milliliter (IU/mL) instead of the formerly used ELISA units per milliliter (ELU/mL). The newly validated DTPa ELISA's used in the study have a lower assay cut-off as compared to the one described in the protocol. The current assay cut-off is 0.057 IU/mL for anti-D, 0.043 IU/mL for anti-T, 2.693 IU/mL for anti-PT, 2.046 IU/mL for anti-FHA and 2.187 IU/mL for anti-PRN. An agreement between the old and new ELISAs was shown with regards to the two thresholds of clinical relevance for the DI/TE response (0.1 IU/mL and 1.0 IU/mL) and therefore the clinical endpoints and anti-D and anti-T are unchanged. In the absence of a correlate of protection for the B. pertussis antigens, the pertussis endpoints were redefined based on the assay cut-off (see section 5.7.5 of protocol).
- In addition, following CBER feedback on the anti-D re-validated assay, a calibration factor of 0.543 was applied in the analysis of anti-D in order to align the ELISA assay to the WHO 10/262 reference samples which are measured as 2 IU/mL by Di neutralization. Assay since 54 WHO 10/262 reference samples measured by GSK re-validated ELISA led to GMC was about two fold (1.841) higher than the expected value (2 IU/mL).

- Note: Due to re-validation of all assays, the cut-offs presented in Table 11 of the protocol of few antigens have changed. Below table has an updated threshold.

Antigen	Threshold for positivity
• Anti-PT	• 2.693 IU/mL
• Anti-FHA	• 2.046 IU/mL
• Anti-PRN	• 2.187 IU/mL
• Anti-D	• 0.057 IU/mL
• Anti-T	• 0.043 IU/mL
• Anti-polio	• 8 dilution
• Anti-PRP	• 0.066 µg/mL
• Anti-HBs	• 6.2 mIU/mL
• Anti-pneumococcal serotypes (1)	• 0.080 µg/mL
• Anti-pneumococcal serotypes (3)	• 0.075 µg/mL
• Anti-pneumococcal serotypes (4)	• 0.061 µg/mL
• Anti-pneumococcal serotypes (5)	• 0.198 µg/mL
• Anti-pneumococcal serotypes (6A)	• 0.111 µg/mL
• Anti-pneumococcal serotypes (6B)	• 0.102 µg/mL
• Anti-pneumococcal serotypes (7F)	• 0.063 µg/mL
• Anti-pneumococcal serotypes (9V)	• 0.066 µg/mL
• Anti-pneumococcal serotypes (14)	• 0.160 µg/mL
• Anti-pneumococcal serotypes (18C)	• 0.111 µg/mL
• Anti-pneumococcal serotypes (19A)	• 0.199 µg/mL
• Anti-pneumococcal serotypes (19F)	• 0.163 µg/mL
• Anti-pneumococcal serotypes (23F)	• 0.073 µg/mL

10. LIST OF FINAL REPORT TABLES, LISTINGS AND FIGURES

The TFL TOC (Tables Figures and Listings Table Of Contents) provides the list of tables/listings and figures needed for the study report (synopsis, in-text, post-text) and for public disclosure (CTRS).

The following group names will be used in the TFLs:

Group order in tables	Group label in tables	Group definition for footnote	Pooled Groups label in tables	Pooled definition for footnote
1	dTpa Group	Infants born to mothers belonging to the dTpa Group in study 116945 [DTPA (BOOSTRIX)-047] where mothers received dTpa during pregnancy. All subjects in this group will receive Infanrix hexa co-administered with Prevenar 13 according to the routine national immunisation schedule.	NA	NA
2	Control Group	Infants born to mothers belonging to the Control group in study 116945 [DTPA (BOOSTRIX)-047] where mothers received placebo during pregnancy. All subjects in this group will receive Infanrix hexa co-administered with Prevenar 13 according to the routine national immunisation schedule.	NA	NA

Tables will be generated on ATP cohort for immunogenicity with the following sub-group names inherited from the study 116945 [DTPA (BOOSTRIX)-047]

Sub-group order in tables	Sub-group label in tables	Sub-group definition for footnote
1	18-24Y	18-24 years old subjects
2	25-34Y	25-34 years old subjects
3	35-45Y	35-45 years old subjects
4	27-32W	27-32 weeks of gestation of foetus at dose 1
5	33-36W	33-36 weeks of gestation of foetus at dose 1

11. ANNEX 1 STANDARD DATA DERIVATION RULE AND STATISTICAL METHODS

11.1. Statistical Method References

- The exact two-sided 95% CIs for a proportion within a group will be the Clopper-Pearson exact CI [Clopper CJ, Pearson ES. The use of confidence or fiducial limits illustrated in the case of binomial. *Biometrika*. 1934; 26:404-413].
- The 95% CI for geometric mean titers/concentrations (GMTs/GMCs) will be obtained within each group separately. The 95% CI for the mean of log-transformed titer/concentration will be first obtained assuming that log-transformed values were normally distributed with unknown variance. The 95% CI for the GMTs/GMCs will be then obtained by exponential-transformation of the 95% CI for the mean of log-transformed titer/concentration.

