In line with these recommendations, study 116945 [DTPA (BOOSTRIX)-047] will be conducted to evaluate the immunogenicity and safety of GlaxoSmithKline (GSK) Biologicals' dTpa vaccine, *Boostrix*, in pregnant women, ***as well as the transfer of maternal antibodies against pertussis to the foetus (cord blood sample at delivery)***. Subjects will receive a dose of *Boostrix* during pregnancy or immediately post-delivery. **(Amended 06 September 2016)**

All infants born to pregnant women who participate in study 116945 [DTPA (BOOSTRIX)-047] will be offered enrolment in the present study. This study will be conducted to evaluate the immunogenicity and safety of GSK Biologicals' combined diphtheria-tetanus-acellular pertussis-hepatitis B-inactivated poliovirus and *Haemophilus influenzae* type b vaccine (DTPa-HBV-IPV/Hib), *Infanrix hexa*, given in the primary vaccination schedule. This will help us evaluate if the presence of transplacentally transferred maternal antibodies interfere with the immune response to primary vaccination with *Infanrix hexa* and a co-administered pneumococcal conjugate vaccine given as a part of this study in infants.

The following section outlines the risk assessment and mitigation strategy for this study protocol:

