10.3. Determination of sample size

The sample size for this study is not derived from any power based calculation. The sample size would consist of all infants whose mothers were enrolled in the study 116945 [DTPA (BOOSTRIX)-047]. Considering approximately 10%-30% reduction in the number of evaluable subjects due to drop-outs and protocol violations from the initial

study, the table below gives the estimated sample size of evaluable subjects that can be expected and the precision achieved with this sample for various expected values.

Table 22 Exact 95% CI of the different values of observed response rate (vaccine response rate or seroprotection rate) for a sample size of 238-300 subjects)

Number of evaluable subjects	Observed response rate expressed as a percentage	Exact 2-sided 95% CI for this observed rate for a sample size of 300 subjects	
		Lower Limit (LL)	Upper Limit (UL)
300	70	64.5	75.1
	75	69.7	79.8
	80	75.0	84.4
	85	80.4	88.8
	92	88.3	94.8
	93	89.5	95.6
	94	90.7	96.4
	95	91.9	97.2
	96	93.1	97.9
	97	94.4	98.6
	98	95.7	99.3
	99	97.1	99.8
272	70	64.4	75.6
	75	69.4	80.0
	80	74.9	84.7
	85	80.5	89.3
	92	88.4	95.2
	93	89.3	95.7
	94	90.6	96.6
	95	92.0	97.4
	96	92.9	98.0
	97	94.3	98.7
	98	95.8	99.4
	99	97.4	99.9
238	70	63.9	75.9
	75	69.2	80.6
	80	74.6	85.1
	85	80.1	89.5
	92	87.8	95.1
	93	89.3	96.1
	94	90.3	96.7
	95	91.4	97.4
	96	92.9	98.3
	97	94.0	98.8
	98	95.8	99.5
	99	97.0	99.9
	100	98.5	100.0

Reference study:

217744/070: Group receiving DTPa-HBV-IPV/Hib full-term infants according to 2, 4, 6 schedule in Spain.

217744/078: Group receiving DTPa-HBV-IPV/Hib +Prevenar according to 2, 3, 4 schedule in Germany.

217744/054: Group receiving DTPa-HBV-IPV/Hib according to 3,5,11 schedule in Italy and Germany [Hardy-Fairbanks, 2013]. Based on this reference, the confidence interval of lower response rate also included in case of any immune interference.

The reference values are presented in [Table 23](#).

CONFIDENTIAL

201330 [DTPA (BOOSTRIX)-048 PRI]
Protocol Amendment 1 Final

Table 23 Reference values

Study Group	Schedule (months)	N	D	T	PT VR	FHA VR	PRN VR	HBs	POLIO TYPE 1	POLIO TYPE 2	POLIO TYPE 3	PRP
217744/070												
DTPa-HBV-IPV/Hib pre-term	2,4,6	93	100	100	98.9	100	100	93.4	100	100	100	92.5
DTPa-HBV-IPV/Hib full-term	2,4,6	89	100	100	98.9	100	98.9	95.2	100	100	100	97.8
217744/078												
DTPa-HBV-IPV/Hib	2,3,4	138	100	100	100	97.8	97.8	97.8	100	98.4	99.2	95.7

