Table 1 Study groups and epoch foreseen in the study

Study Groups	Number of subjects	Age (Min - Max)*	Epoch
			Epoch 001
dTpa Group	340	6-14 weeks	x
Control Group	340	6-14 weeks	x

*Up to and including 14 weeks and 6 days of age.

The study groups and treatment foreseen in the study are presented in Table 2.

Table 2 Study groups and treatments foreseen in the study

Treatment names	Vaccine name	Study Groups	
		dTpa Group	Control Group
Infanrix hexa	DTPa-HBV-IPV	x	x
	Hib	x	x
Prevenar 13	Prevenar 13	x	x

- Control: uncontrolled
- Vaccination schedules: All subjects will receive either 3 doses of *Infanrix hexa* co-administered with *Prevenar 13** at 2, 4 and 6 months or 2, 3 and 4 months, either 2 doses of *Infanrix hexa* co-administered with *Prevenar 13* at 3 and 5 months or 2 and 4 months, depending on the immunisation schedule of the country.

*In some countries/regions with an *Infanrix hexa* 3 doses routine national immunisation schedule, *Prevenar 13* could be administered as 2-doses or 3-doses primary vaccination schedule (according to the routine national immunisation schedule).

- Treatment allocation: non-randomised. All subjects will receive *Infanrix hexa* co-administered with *Prevenar 13*.
- Blinding: Open-label. Note: The study personnel operating GSK Biologicals' randomisation system on internet (SBIR) and the site staff will remain blinded towards the treatment allocation to subjects in study 116945 [DTPA (BOOSTRIX)-047].
- The blinding of study epoch is presented in Table 3.

Table 3 Blinding of study epoch

Study Epoch	Blinding
Epoch 001	open

- Sampling schedule: Blood samples will be drawn from all subjects at the following timepoints:
 - Pre-Pri: Before the first *Infanrix hexa* vaccine administration, a volume of approximately 2 mL of whole blood (to provide approximately 0.7 mL of serum) will be collected from all study participants.
 - Post-Pri: One month after the last dose of *Infanrix hexa* primary vaccination, approximately 5 mL of whole blood (to provide approximately 1.7 mL of serum) will be collected from all study participants.
- Type of study: extension of other protocol(s) 116945 [DTPA (BOOSTRIX)-047].
- Data collection: Electronic Case Report Form (eCRF).

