6.3. Immunogenicity

6.3.1. Analysis of immunogenicity planned in the protocol

The primary analysis will be based on the ATP cohort for analysis of immunogenicity. If in any vaccine group, the percentage of enrolled subjects excluded from this ATP cohort is more than 5%, a second analysis based on the TVC will be performed to complement the ATP analysis. All analyses will be descriptive. For each group, at each timepoint that a blood sample result is available:

- Seropositivity rates against PT, FHA and PRN antigens and pneumococcal antigens (1, 3, 4, 5, 6A, 6B, 7F, 9V, 14, 18C, 19A, 19F, 23F) with exact 95% CI [Clopper, 1934] will be calculated.
- Seroprotection rates against diphtheria toxoid, tetanus toxoid, HBs, PRP antigen and poliovirus types 1, 2, 3 antigens (with exact 95% CI [Clopper, 1934]) will be calculated.
- Percentage of subjects with anti-pneumococcal serotypes (1, 3, 4, 5, 6A, 6B, 7F, 9V, 14, 18C, 19A, 19F, 23F) antibody concentrations, depending on the GSK laboratory or WHO reference laboratory assay cut-offs, will be calculated along with its exact 95% CI [Clopper, 1934].
- Percentage of subjects with anti-D and anti-T antibody concentrations ≥ 1.0 IU/mL will be calculated along with its exact 95% CI [Clopper, 1934].
- Percentage of subjects with anti-PRP antibody concentrations ≥ 1.0 $\mu\text{g/mL}$ and anti-HBs antibody concentrations ≥ 100 mIU/mL will be calculated along with its exact 95% CI [Clopper, 1934].
- GMC/GMT with 95% CI will be tabulated for antibodies against each antigen.

For serology results one month after last vaccination dose:

- The vaccine response rates to PT, FHA and PRN (with exact 95% CI) will be calculated.
- The distribution of antibody concentrations/titres for each antigen will be displayed using reverse cumulative distribution curves (RCCs).
- The distribution of antibody concentrations or titres of each antigen will be tabulated.

Additional summaries will be provided based on country.

Handling of missing data:

For a given subject and a given immunogenicity measurement, missing or non-evaluable measurements will not be replaced. Therefore, an analysis will exclude subjects with missing or non-evaluable measurements.

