6.3.2. Additional considerations

Considering that RCC are available and the percentage of subjects with titres/concentration above key thresholds are available, the distribution of antibody concentrations or titres of each antigen will not be tabulated.

In addition to the percentage of seroprotected or seropositive subjects, the percentage of subjects above the following cut-off will be summarized

- Anti-PRP antibody concentrations $\geq 1.0 \mu\text{g/mL}$.
- Anti-diphtheria antibody concentrations $\geq 1.0 \text{ IU/mL}$.
- Anti-tetanus antibody concentrations $\geq 1.0 \text{ IU/mL}$.
- Anti-HBs antibody concentrations $\geq 100 \text{ mIU/mL}$.
- Anti-pneumococcal serotypes (1, 3, 4, 5, 6A, 6B, 7F, 9V, 14, 18C, 19A, 19F, 23F) $\geq 0.35 \mu\text{g/mL}$.

In light of the number of subjects enrolled in each country, the analysis by country will be replaced with analysis by schedule (2 doses ie 2,4 months combined with 3,5 months versus 3 doses i.e. 2,3,4 months combined with 2,4,6 months).

In addition subgroups analysis according to gestational age (27-32 weeks and 33-36 weeks) and age of the mother (18-24 year, 25-34 year and 35-45 year) will be performed.

The sub-group analyses will be limited to descriptive tables of GMT/GMC and the percentage of subjects with titres/concentration above key thresholds for ATP cohort of immunogenicity.

SCHEDULE_TXT(Element Text)	country(CTY_NAM)						Total
Frequency Percent Row Pct Col Pct	Australia	Canada	Czechia	Finland	Italy	Spain	
Age group(2, 3, 4 Months)	0 0.00 0.00 0.00	0 0.00 0.00 0.00	71 11.81 100.00 100.00	0 0.00 0.00 0.00	0 0.00 0.00 0.00	0 0.00 0.00 0.00	71 11.81
Age group(2, 4 Months)	0 0.00 0.00 0.00	0 0.00 0.00 0.00	0 0.00 0.00 0.00	0 0.00 0.00 0.00	0 0.00 0.00 0.00	7 1.16 100.00 2.48	7 1.16
Age group(2, 4, 6 Months)	38 6.32 8.32 100.00	144 23.96 31.51 100.00	0 0.00 0.00 0.00	0 0.00 0.00 0.00	0 0.00 0.00 0.00	275 45.76 60.18 97.52	457 76.04
Age group(3, 5 Months)	0 0.00 0.00 0.00	0 0.00 0.00 0.00	0 0.00 0.00 0.00	52 8.65 78.79 100.00	14 2.33 21.21 100.00	0 0.00 0.00 0.00	66 10.98
Total	38 6.32	144 23.96	71 11.81	52 8.65	14 2.33	282 46.92	601 100.00

Deviations from specifications for age and intervals between study visits for subjects vaccinated with *Infanrix hexa* by dose schedule (2 dose schedule and 3 dose schedule separately) will be tabulated.

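### The rationale asks whether maternal antibody interferes with the infant response, but no dTpa-versus-Control difference or ratio is planned; descriptive contrasts would be a cheap improvement

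*SAP*

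**What the plan says.** Protocol 1.2.1 gives the purpose of following these infants: "This will help us evaluate if the presence of transplacentally transferred maternal antibodies interfere with the immune response to primary vaccination" with Infanrix hexa and with the co-administered pneumococcal vaccine. The note under Table 22 in Protocol 10.3 takes up the same idea, saying "the confidence interval of lower response rate also included in case of any immune interference". The table itself gives exact intervals "for a sample size of 238-300 subjects", each for one group's rate.

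The analysis sections stay within group. Protocol 10.7 and SAP 6.3.1 list, for each group and timepoint, seropositivity and seroprotection rates with exact CIs, and "GMC/GMT with 95% CI will be tabulated for antibodies against each antigen". Vaccine response rates and reverse cumulative curves are added after vaccination. SAP 11.1 gives two interval methods: Clopper-Pearson for one proportion and, for geometric means, "The 95% CI for geometric mean titers/concentrations (GMTs/GMCs) will be obtained within each group separately". SAP 6.3.2 adds further thresholds and subgroup tables, and says that "the analysis by country will be replaced with analysis by schedule". Templates 10 to 13 place the groups in separate rows, with no difference or ratio.

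The status of the analysis is equally clear. SAP 6.3.1 says "All analyses will be descriptive", SAP 2 labels the design "Control: uncontrolled", and the objectives in Protocol 2 and SAP 3 speak only of assessing responses.

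**The concern.** Interference can be seen only by comparing infants of mothers vaccinated in pregnancy with infants of mothers vaccinated after delivery. The plan collects the data for that comparison but neither displays it nor says how it would be formed. Anyone who wants the answer must work it out once the results are known, and a contrast added to the report at that stage would appear as unplanned.

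Two separate intervals are also a poor stand-in for the size and precision of a difference, because they can overlap while the interval for the difference excludes zero. Two choices are left open: how dose schedule would enter a contrast, and how to read the pertussis vaccine-response rate when one group is expected to start with more antibody.

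**Working it through.** **1. Table 22 reproduced.** Clopper-Pearson limits for x of n are the 2.5% quantile of Beta(x, n-x+1) and the 97.5% quantile of Beta(x+1, n-x). For 279/300 (93%) they are 89.5 to 95.6, and for 291/300 (97%) 94.4 to 98.6, as printed. All 37 rows reproduce to one decimal, with x the integer at or next to n × rate. The plan's stated precision is therefore that of a single group's rate.

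**2. The same two rows as a contrast.** Newcombe's interval combines the two Wilson intervals.
- Wilson limits: 279/300 gives 89.54 to 95.38; 291/300 gives 94.40 to 98.41.
- Difference: 93 - 97 = -4.0 points.
- Lower limit: -4.0 - √[(93 - 89.54)² + (98.41 - 97)²] = -4.0 - 3.74 = -7.7.
- Upper limit: -4.0 + √[(95.38 - 93)² + (97 - 94.40)²] = -4.0 + 3.52 = -0.5.

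The group intervals overlap between 94.4 and 95.6, but the interval for the difference excludes zero. Miettinen-Nurminen gives -7.8 to -0.5.

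**3. Precision for a difference in rates.** With both groups observed near 95% and n taken from Table 22, the Newcombe half-width is:

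| n per group | half-width, points |
|---|---|
| 238 | 4.15 |
| 272 | 3.89 |
| 300 | 3.65 |

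**4. Precision for a GMC ratio.** The 95% CI is the ratio divided and multiplied by 10^(t × SD × √(2/n)), with t on 2n - 2 degrees of freedom. The documents give no SD of log10 concentration, so 0.4 is assumed, with 0.3 and 0.5 as a range. At n = 238 and SD 0.4: 10^(1.965 × 0.4 × √(2/238)) = 10^0.0721 = 1.180. At 272 it is 1.168 and at 300 it is 1.159. Over n = 238 to 300, SD 0.3 gives 1.13 to 1.12 and SD 0.5 gives 1.23 to 1.20.

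**5. Likely size of the analysed groups.** The schedule table in SAP 6.3.2 totals 601 infants, 601/680 = 88.4% of the target. This counts enrolled infants. The ATP immunogenicity cohort (SAP 5.1.4, 5.2.2 and 5.2.3) still drops infants not born at term, interval deviations, missing Post-Pri serology and codes inherited from the mother. With an even split, assumed because the table is not by group, 601/2 is about 300, so 300 per group is a ceiling. Protocol 10.3 expects a 10% to 30% loss but ties it to the initial study. If that loss is applied to 300 as an assumption, n is 270 to 210. The half-width near 95% is then about 3.9 to 4.4 points. The ratio factor at SD 0.4 is 1.17 to 1.19.

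**6. Schedule.** In the same table, 457 + 71 = 528 infants (87.9%) follow a 3-dose schedule and 7 + 66 = 73 a 2-dose schedule.

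**7. Pertussis rule.** SAP 4.1 counts an initially seropositive infant as a responder if the Post-Pri concentration is at least the Pre-Pri one. The threshold each such infant must reach is thus its own starting value. If dTpa infants start higher, they face a higher bar even with identical Post-Pri distributions. Template 13 separates seronegative from seropositive infants, but starting values can still differ between groups within the seropositive stratum, so the split does not remove the effect. The documents give no figures from which to size it.

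**The case against.** The strongest reply is that the plan is a consistent descriptive design. No objective or endpoint states a comparison, the sample size has no power basis, and the design is labelled uncontrolled and non-randomised. The rationale promises only to help evaluate interference. All of that stands. It rules out calling the gap a contradiction, but not a descriptive difference with a CI, which needs no hypothesis or margin.

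Readers can also derive an unadjusted contrast from n, N and the GMC intervals. That stands too. With cohort, endpoints and timepoints fixed, an unadjusted contrast leaves little room for data-driven choice. A schedule-adjusted ratio is harder to recover from published tables.

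Schedule and starting serostatus are not ignored: by-schedule tables and the Template 13 split are planned. What is missing is how either would enter a contrast.

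A reader might infer that the sponsor would judge interference by whether intervals overlap, and so would miss real differences at a calculable rate. The documents set no overlap rule, so step 2 only illustrates what the display leaves unseen.

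Finally, this is a claim of absence on incomplete text. Protocol 10.9 is in the table of contents but its text was not available. The TFL TOC, which lists the report tables, is a separate document.

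**Conclusion.** The point holds as a cheap improvement. The supplied plan gives within-group rates, GMC/GMTs and curves, and no between-group estimate for the question the rationale raises. At 238 to 300 evaluable infants per group, the data could give a rate difference near 95% to about ±4.2 to 3.7 points, and a GMC ratio to a factor of about 1.18 to 1.16. At an assumed 210 to 270 per group the figures are about ±4.4 to 3.9 points and 1.19 to 1.17. The ratio factors rest on an assumed log10 SD of 0.4, and the rate figures on observed rates near 95%.

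A reader might go further and conclude that the study fails its primary objective or that its analysis is invalid. The documents do not support that: the objective is to assess responses, and the within-group analysis does so. Nor do they show that the vaccine-response rule will produce a false signal of any given size, because that depends on concentrations the documents do not report.

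**What to change.** In SAP 6.3.2 and 11.1, and as extra columns in the planned tables, add for the Post-Pri timepoint:

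- the dTpa minus Control difference in D, T, HBs, polio 1 to 3 and PRP seroprotection, in PT, FHA and PRN seropositivity, and in PT, FHA and PRN vaccine response, each with a two-sided 95% CI for a difference in proportions, for example Miettinen-Nurminen;
- the unadjusted dTpa/Control GMC or GMT ratio for every antigen, with a 95% CI from the log10 values, and a version adjusted for 2-dose versus 3-dose schedule for the Infanrix hexa antigens.

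For pertussis, present the Post-Pri GMC ratio beside vaccine response. Footnote that the rule sets a higher bar for infants who start higher and that the serostatus split does not remove this.

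Label every contrast descriptive, with no test, margin or multiplicity control. Note that enrolled and ATP infants are a subset of the mothers' allocation. Pre-Pri contrasts are optional.

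The cost is SAP wording and table columns, with no new data. There would be 7 + 3 + 3 = 13 rate differences and 10 + 13 = 23 ratios, so 36 main contrasts, plus 10 schedule-adjusted ratios. If there were no effect anywhere, about 0.05 × 36 = 1.8 of the 36 would exclude it by chance, which is why the descriptive label is needed.
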